5.5 Definition of Dose-Limiting Toxicity

Pembrolizumab and radiation have been evaluated previously specifically in patients with SCCHN. However, although this is not a phase I protocol, the use of pembrolizumab in combination with high and low dose radiation is relatively novel, and therefore we plan to include a safety-run-in to ensure that treatment is well tolerated in this setting.

Dose-limiting toxicity (DLT) is based on the CTEP Active Version of the NCI Common Terminology Criteria for Adverse Events (CTCAE). DLT refers to toxicities experienced between the start of treatment and cycle 3, day 1 of pembrolizumab (the DLT evaluation period). A DLT will be defined as follows:

DLTs will be graded according to the National Cancer Institute's CTCAE v4.0 (<http://ctep.cancer.gov/forms/CTCAEv4.pdf>). A DLT is any event that: a) occurs during the DLT evaluation period; and b) is possibly, probably, or definitely related to the administration of pembrolizumab and radiation; and c) fulfills any of the following criteria:

1. Any Grade ≥ 3 pneumonitis, neurological event or uveitis.
2. Any Grade 2 pneumonitis, neurological event or uveitis, with the *following exception*:
 - Grade 2 pneumonitis, neurological event or uveitis that downgrade to Grade ≤ 1 within 3 days after onset, whereby maximal supportive care, including systemic corticosteroids, is permitted.
3. Any *other* Grade ≥ 3 toxicity, with the *following exceptions*:
 - Grade 3 irAEs that downgrade to Grade ≤ 2 within 3 days, or to Grade ≤ 1 or baseline within 14 days after onset, whereby maximal supportive care, including systemic corticosteroids, is permitted.
 - Grade 3 colitis that downgrades to Grade ≤ 2 within 7 days after onset, whereby maximal supportive care, including systemic corticosteroids, is permitted.

CONFIDENTIAL

This document is confidential. Do not disclose or use except as authorized.

- Grade 3 asymptomatic endocrinopathy, managed with or without systemic corticosteroid therapy and/or hormone replacement therapy.
- Grade 3 inflammatory reaction attributed to a local antitumor response (e.g., inflammatory reaction at sites of metastatic disease, lymph nodes, etc.).
- Grade 3 fatigue for \leq 7 days.
- Grade 3 infusion-related reaction (first occurrence and in the absence of steroid prophylaxis) that resolves within 6 hours with appropriate clinical management.
- Liver transaminase elevation \leq 8 times ULN that downgrades to Grade \leq 2 (\leq 5 times ULN) within 7 days after onset, whereby maximal supportive care, including systemic corticosteroids, is permitted.
- Total bilirubin \leq 5 times ULN that downgrades to Grade \leq 2 (\leq 3 times ULN) within 7 days after onset, whereby maximal supportive care, including systemic corticosteroids, is permitted.
- Grade \geq 3 neutropenia that (1) is not associated with fever or systemic infection, (2) does not require medical intervention, and (3) improves to Grade 2 within 7 days.
- Grade 3 and 4 lymphopenia.
- Grade 3 thrombocytopenia that (1) is not associated with clinically significant bleeding, (2) does not require medical intervention, and (3) improves to Grade 2 within 7 days.
- Isolated Grade 3 electrolyte abnormalities that are not associated with clinical signs or symptoms and are reversed with appropriate maximal medical intervention within 3 days.
- Any pre-existing laboratory abnormality that deteriorates to Grade 3/4, but where the increment of deterioration is considered not clinically significant by both investigator and sponsor.

Immune-related AEs (irAEs) are defined as AEs of immune nature (i.e., inflammatory) in the absence of a clear alternative etiology. In the absence of clinical abnormality, repeat laboratory testing will be conducted to confirm significant laboratory findings prior to designation as a DLT.

While rules for adjudicating DLTs are specified above, an AE that is Grade $<$ 3 or listed as exempt above may also be defined as a DLT after consultation with the sponsor and Investigators, based on the emerging safety profile of pembrolizumab. Likewise, subjects who become not evaluable for DLT because they discontinued or interrupted treatment due to toxicities other than DLTs may be counted as DLT subjects.

5.6 General Concomitant Medication and Supportive Care Guidelines

5.6.1 Concomitant Medication Guidelines

Medications or vaccinations specifically prohibited in the exclusion criteria are not allowed during the ongoing trial. If there is a clinical indication for one of these or other medications or vaccinations specifically prohibited during the trial, discontinuation from trial therapy or vaccination may be required. The investigator should discuss any questions regarding this with the Merck Clinical team. The final decision on any supportive therapy or vaccination rests with the investigator and/or the subject's primary physician.

Acceptable Concomitant Medications

All treatments that the investigator considers necessary for a subject's welfare may be administered at the discretion of the investigator in keeping with the community standards of medical care. All

CONFIDENTIAL

This document is confidential. Do not disclose or use except as authorized.

concomitant medication will be recorded on the case report form (CRF) including all prescription, over-the-counter (OTC), herbal supplements, and IV medications and fluids. If changes occur during the trial period, documentation of drug dosage, frequency, route, and date may also be included on the CRF.

All concomitant medications received within 28 days before the first dose of trial treatment and 30 days after the last dose of trial treatment should be recorded. Concomitant medications administered after 28 days after the last dose of trial treatment should be recorded for SAEs as specified in Section 7.2.

Prohibited Concomitant Medications

Subjects are prohibited from receiving the following therapies during the Screening and Treatment Phase of this trial:

- Antineoplastic systemic chemotherapy or biological therapy
- Immunotherapy not specified in this protocol
- Investigational agents other than pembrolizumab
- Radiation therapy not specified in this protocol
- Any systemically active oral, injected, or implanted hormonal method of contraception except for progesterone coated intrauterine devices (IUDs) that had been previously implanted.
- Live vaccines within 30 days prior to the first dose of trial treatment and while participating in the trial. Examples of live vaccines include, but are not limited to, the following: measles, mumps, rubella, varicella/zoster, yellow fever, rabies, BCG, and typhoid vaccine.
- Systemic glucocorticoids for any purpose other than to modulate symptoms from radiation or an event of clinical interest of suspected immunologic etiology. The use of physiologic doses of corticosteroids may be approved after consultation with the Sponsor.

Subjects who, in the assessment by the investigator, require the use of any of the aforementioned treatments for clinical management should be removed from the trial. Subjects may receive other medications that the investigator deems to be medically necessary.

There are no prohibited therapies during the Post-Treatment Follow-up Phase.

5.6.2 Supportive Care Guidelines – general medications

The following treatments are permitted throughout the duration of the study treatment phase and during follow-up:

- Standard therapies for pre-existing medical conditions unless listed as prohibited therapy below. Any medication intended solely for supportive care (e.g., analgesics, anti-diarrheal, anti-depressants) may be used at the investigator's discretion. Antiemetics and anti-diarrheal medications should not be administered prophylactically before initial treatment with study drugs. At the discretion of the investigator, prophylactic antiemetic and anti-diarrheal medication(s) may

CONFIDENTIAL

This document is confidential. Do not disclose or use except as authorized.

be used as per standard clinical practice before subsequent doses of study drugs or before, during or after radiation treatment.

- Anticoagulants - Anticoagulation with heparin, heparin derivatives, and/or warfarin may be given at the discretion of the treating physician. Coagulation parameters should be checked at least once monthly, or more frequently at discretion of treating physician.
- Pain medications administered per standard clinical practice are acceptable while the patient is enrolled in the study.

Patients who experience toxicities should be treated symptomatically as clinically indicated. Medications that are considered necessary for the subject's welfare and that are not expected to interfere with the evaluation of study treatment or be restricted may be given at the discretion of the investigator. Ancillary treatments will be given as medically indicated.

5.7 Contraception, Pregnancy and Nursing considerations

5.7.1 Contraception

Pembrolizumab may have adverse effects on a fetus in utero. Furthermore, it is not known if pembrolizumab has transient adverse effects on the composition of sperm.

For this trial, male subjects will be considered to be of non-reproductive potential if they have azoospermia (whether due to having had a vasectomy or due to an underlying medical condition). Female subjects will be considered of non-reproductive potential if they are either:

- (1) postmenopausal (defined as at least 12 months with no menses without an alternative medical cause; in women < 45 years of age a high follicle stimulating hormone (FSH) level in the postmenopausal range may be used to confirm a post-menopausal state in women not using hormonal contraception or hormonal replacement therapy. In the absence of 12 months of amenorrhea, a single FSH measurement is insufficient.);

OR

- (2) have had a hysterectomy and/or bilateral oophorectomy, bilateral salpingectomy or bilateral tubal ligation/occlusion, at least 6 weeks prior to screening;

OR

- (3) has a congenital or acquired condition that prevents childbearing.

Female and male subjects of reproductive potential must agree to avoid becoming pregnant or impregnating a partner, respectively, while receiving study drug and for 120 days after the last dose of study drug by complying with one of the following:

- (1) practice abstinence[†] from heterosexual activity;

OR

- (2) use (or have their partner use) acceptable contraception during heterosexual activity.

Acceptable methods of contraception are[‡]:

Single method (one of the following is acceptable):

- intrauterine device (IUD)
- vasectomy of a female subject's male partner
- contraceptive rod implanted into the skin

Combination method (requires use of two of the following):

- diaphragm with spermicide (cannot be used in conjunction with cervical cap/spermicide)
- cervical cap with spermicide (nulliparous women only)
- contraceptive sponge (nulliparous women only)
- male condom or female condom (cannot be used together)
- hormonal contraceptive: oral contraceptive pill (estrogen/progestin pill or progestin-only pill), contraceptive skin patch, vaginal contraceptive ring, or subcutaneous contraceptive injection

†Abstinence (relative to heterosexual activity) can be used as the sole method of contraception if it is consistently employed as the subject's preferred and usual lifestyle and if considered acceptable by local regulatory agencies and IRB. Periodic abstinence (e.g., calendar, ovulation, sympto-thermal, post-ovulation methods, etc.) and withdrawal are not acceptable methods of contraception.

‡If a contraceptive method listed above is restricted by local regulations/guidelines, then it does not qualify as an acceptable method of contraception for subjects participating at sites in this country/region.

Subjects should be informed that taking the study medication may involve unknown risks to the fetus (unborn baby) if pregnancy were to occur during the study. In order to participate in the study subjects of childbearing potential must adhere to the contraception requirement (described above) 14 days prior to the initiation of study medication throughout the study period up to 4 months after the last dose of trial therapy. If there is any question that a subject of childbearing potential will not reliably comply with the requirements for contraception, that subject should not be entered into the study.

5.7.2 Use in Pregnancy

If a subject inadvertently becomes pregnant while on treatment with pembrolizumab, the subject will immediately be removed from the study. The site will contact the subject at least monthly and document the subject's status until the pregnancy has been completed or terminated. The outcome of the pregnancy will be reported to the Sponsor and to Merck without delay and within 24 hours to the Sponsor and within 2 working days to Merck if the outcome is a serious adverse experience (e.g., death, abortion, congenital anomaly, or other disabling or life-threatening complication to the mother or newborn).

The study investigator will make every effort to obtain permission to follow the outcome of the pregnancy and report the condition of the fetus or newborn to Merck. If a male subject impregnates his female partner the study personnel at the site must be informed immediately and the pregnancy reported to Merck and followed as described above.

5.7.3 Use in Nursing Women

It is unknown whether pembrolizumab is excreted in human milk. Since many drugs are excreted in human milk, and because of the potential for serious adverse reactions in the nursing infant, subjects who are breast-feeding are not eligible for enrollment.

CONFIDENTIAL

This document is confidential. Do not disclose or use except as authorized.

5.8 Criteria for Taking a Participant Off Protocol Therapy

Duration of therapy will depend on individual response, evidence of disease progression and tolerance. In the absence of treatment delays due to adverse event(s), treatment may continue until one of the following criteria applies:

- Disease progression. In the case of progressive disease, confirmatory scans are recommended between 4-8 weeks following the date of initial progression along with continued treatment, provided the patient is thought to be deriving clinical benefit and is counseled regarding the risks and benefits of continued treatment. If progression is confirmed, date of progression is dated at the time of the original scans. If progression is confirmed, continued treatment is only allowed if irRC demonstrates a response or stable disease, again provided the patient is thought to be clinically benefitting and is counseled regarding the risk and benefits of remaining on treatment.
- Intercurrent illness that prevents further administration of treatment
- Unacceptable adverse event(s)
- Participant demonstrates an inability or unwillingness to comply with the oral medication regimen and/or documentation requirements
- Participant decides to withdraw from the protocol therapy
- General or specific changes in the participant's condition render the participant unacceptable for further treatment in the judgment of the treating investigator

Participants will be removed from the protocol therapy when any of these criteria apply. The reason for removal from protocol therapy, and the date the participant was removed, must be documented in the case report form (CRF). Alternative care options will be discussed with the participant.

A Treatment Ended/Off Study Form will be filled out within OnCore, when a participant is removed from protocol therapy.

In the event of unusual or life-threatening complications, treating investigators must immediately notify the Overall PI, [name] at [name] (pager #).

5.9 Duration of Follow Up

Participants removed from protocol therapy will be followed for overall survival, every 6 months, until death (by phone).

Given pembrolizumab has become standard of care for patients with recurrent / metastatic SCCHN, patients on study who proceed with treatment locally outside of a study center should have medical records and scans obtained on a regular basis to monitor for date of progression / response.

CONFIDENTIAL

This document is confidential. Do not disclose or use except as authorized.

Participants removed from protocol therapy for unacceptable adverse event(s) will be followed until resolution or stabilization of the adverse event. For these patients, scans should be performed every 6 weeks for 1 year.

5.10 Criteria for Taking a Participant Off Study

Participants will be removed from study when any of the following criteria apply:

- Lost to follow-up
- Withdrawal of consent for data submission
- Death

The reason for taking a participant off study, and the date the participant was removed, must be documented in the case report form (CRF).

For Centralized Subject Registrations, the research team submits a completed Off Treatment/Off Study form to ODQ when a participant comes off study. This form can be found on the ODQ website or obtained from the ODQ registration staff.

For Decentralized Subject Registrations, the research team updates the relevant Off Treatment/Off Study information in OnCore.

In the event of unusual or life-threatening complications, participating investigators must immediately notify the Principal Investigator, [name], MPH at Partners pager [name].

6. DOSING DELAYS/DOSE MODIFICATIONS

Dose delays and modifications will be made as indicated in the following table(s). The descriptions and grading scales found in the revised NCI Common Terminology Criteria for Adverse Events (CTCAE) version 4.0 will be utilized for dose delays and dose modifications. A copy of the CTCAE version 4.0 can be downloaded from the CTEP website

http://ctep.cancer.gov/protocolDevelopment/electronic_applications/ctc.htm.

If possible, symptoms should be managed symptomatically. In the case of toxicity, appropriate medical treatment should be used (including anti-emetics, anti-diarrheals, etc.).

All adverse events experienced by participants will be collected from the time of the first dose of study treatment, through the study and within 30 days of the last study intervention. Participants continuing to experience toxicity at the last scheduled study visit may be kept on the study until the toxicity has resolved or is deemed irreversible.

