5.3.2 End-of-Treatment Procedures

End-of-Treatment Visit

All subjects will be asked to return to the site for a final, End-of-Treatment visit, if possible. This visit must be performed within 30 days of final administration of study treatment. End-of-treatment assessments will not have to be repeated if the same assessments were performed within 7 days of this visit.

Record:

- For patients who come off for reasons other than progressive disease: Tumor assessments to be performed every 6 weeks if patients come off within one year of therapy. If study treatment is discontinued due to PD, then tumor assessments are not required for that subject.
- ECOG PS
- Physical exam
- Vital signs and weight
- Concomitant medication use
- AEs or SAEs

Draw blood sample for:

- Hematology (Table 2)
- Chemistry panel (Table 2)

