6.2 Management of toxicities attributable to pembrolizumab

Adverse events (both non-serious and serious) associated with pembrolizumab exposure may represent an immunologic etiology. These adverse events may occur shortly after the first dose or several months after the last dose of treatment. Pembrolizumab must be withheld for drug-related toxicities and severe or life-threatening AEs as per Table 4 below.

Table 4: Dose modification guidelines for Pembrolizumab for drug-related adverse events

Toxicity	Hold Treatment For Grade	Timing for Restarting Treatment	Discontinue Subject
Diarrhea/Colitis	2-3	Toxicity resolves to Grade 0-1.	Toxicity does not resolve within 12 weeks of last dose or inability to reduce corticosteroid to 10 mg or less of prednisone or equivalent per day within 12 weeks.
	4	Permanently discontinue	Permanently discontinue
AST, ALT, or Increased Bilirubin	2	Toxicity resolves to Grade 0-1	Toxicity does not resolve within 12 weeks of last dose.
	3-4	Permanently discontinue (see exception below) ¹	Permanently discontinue
Type 1 diabetes mellitus (if new onset) or Hyperglycemia	T1DM or 3-4	Hold pembrolizumab for new onset Type 1 diabetes mellitus or Grade 3-4 hyperglycemia associated with evidence of beta cell failure.	Resume pembrolizumab when patients are clinically and metabolically stable.
Hypophysitis	2-3	Toxicity resolves to Grade 0-1	Toxicity does not resolve within 12 weeks of last dose or inability to reduce corticosteroid to 10 mg or

CONFIDENTIAL

This document is confidential. Do not disclose or use except as authorized.

Toxicity	Hold Treatment For Grade	Timing for Restarting Treatment	Discontinue Subject
			less of prednisone or equivalent per day within 12 weeks.
	4	Permanently discontinue	Permanently discontinue
Hyperthyroidism	3	Toxicity resolves to Grade 0-1	Toxicity does not resolve within 12 weeks of last dose or inability to reduce corticosteroid to 10 mg or less of prednisone or equivalent per day within 12 weeks.
	4	Permanently discontinue	Permanently discontinue
Hypothyroidism	2-4	Therapy with pembrolizumab can be continued while treatment for the thyroid disorder is instituted	Therapy with pembrolizumab can be continued while treatment for the thyroid disorder is instituted.
Infusion Reaction	3-4	Permanently discontinue	Permanently discontinue

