7.8.4 Reporting Requirements for Merck

Any serious adverse event, or follow up to a serious adverse event, including death due to any cause other than progression of the cancer under study that occurs to any subject from the time the consent is signed through 30 days following cessation of treatment, or the initiation of new anti-cancer therapy, whichever is earlier, whether or not related to Merck product, must be reported within 2 working days to Merck Global Safety.

Non-serious Events of Clinical Interest will be forwarded to Merck Global Safety and will be handled in the same manner as SAEs.

Additionally, any serious adverse event, considered by an investigator who is a qualified physician to be related to Merck product that is brought to the attention of the investigator at any time outside of the time period specified in the previous paragraph also must be reported immediately to Merck.

SAE reports and any other relevant safety information are to be forwarded to the Merck Global Safety [contact]

A copy of all 15 Day Reports and Annual Progress Reports is submitted as required by FDA, European Union (EU), Pharmaceutical and Medical Devices agency (PMDA) or other local regulators. Investigators will cross reference this submission according to local regulations to the Merck Investigational Compound Number (IND, CSA, etc.) at the time of submission. Additionally, investigators will submit a copy of these reports to Merck & Co., Inc. (Attn: Worldwide Product Safety; [contact]) at the time of submission to FDA.

All subjects with serious adverse events must be followed up for outcome.

CONFIDENTIAL

This document is confidential. Do not disclose or use except as authorized.

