7.8.5 Events of Clinical Interest (ECIs)

Selected non-serious and serious adverse events are also known as Events of Clinical Interest (ECI) and must be recorded as such on the Adverse Event case report forms/worksheets and reported within 24 hours to the Sponsor and within 2 working days to Merck Global Safety. (Attn: Worldwide Product Safety; [contact]). Events of clinical interest for this trial include:

1. an overdose of Merck product, as defined in Section 7.7.3 - Definition of an Overdose for This Protocol and Reporting of Overdose to Merck, that is not associated with clinical symptoms or abnormal laboratory results.
2. an elevated AST or ALT lab value that is greater than or equal to 3X the upper limit of normal and an elevated total bilirubin lab value that is greater than or equal to 2X the upper limit of normal and, at the same time, an alkaline phosphatase lab value that is less than 2X the upper limit of normal, as determined by way of protocol-specified laboratory testing or unscheduled laboratory testing.*

***Note:** These criteria are based upon available regulatory guidance documents. The purpose of the criteria is to specify a threshold of abnormal hepatic tests that may require an additional evaluation for an underlying etiology. The trial site guidance for assessment and follow up of these criteria can be found in the Investigator Trial File Binder (or equivalent).

Additional adverse events:

A full document entitled “Event of Clinical Interest Guidance Document” (previously entitled, “Event of Clinical Interest and Immune-Related Adverse Event Guidance Document”), which provides guidance regarding identification, evaluation and management of ECIs and irAEs, is in the possession of the PI and can be accessed upon request.

ECIs (both non-serious and serious adverse events) identified from the date of first dose through 90 days following cessation of treatment, or 30 days after the initiation of a new anticancer therapy, whichever is earlier, need to be reported within 24 hours to the Sponsor and within 2 working days to Merck Global Safety. (Attn: Worldwide Product Safety; [contact]), regardless of attribution to study treatment, consistent with standard SAE reporting guidelines.

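### ECIs must be recorded to 90 days after treatment, but no safety review is scheduled after the end-of-treatment visit, so late ECIs after progression are found only passively

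*Combined protocol and SAP*

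**What the plan says.** **End of the windows.** Section 6 collects all adverse events (AEs) from the first dose "through the study and within 30 days of the last study intervention". A participant with toxicity still present at the last visit "may be kept on the study until the toxicity has resolved or is deemed irreversible". Section 7.8.5 sets a longer window for ECIs, whether serious or not and whatever their attribution: "through 90 days following cessation of treatment, or 30 days after the initiation of a new anticancer therapy, whichever is earlier". It adds that ECIs "must be recorded as such on the Adverse Event case report forms/worksheets".

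**Scheduled reviews.** Section 5.3.2 lists AEs among the items for the end-of-treatment visit: "This visit must be performed within 30 days of final administration of study treatment". Section 7.8.5 ties ECI assessment to the time before each dose. Section 5.3.3 requires tumor assessments every 6 weeks for patients who stop without progressive disease (PD) and lists no AE review with them. Section 5.9 follows patients who stopped for toxicity until that event resolves or stabilizes, with scans every 6 weeks for a year. Under Section 5.3.2, patients who stop for PD need no further tumor assessments. What remains for them is the survival follow-up by phone every 6 months (Section 5.9; Table 8 notes i and m).

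**Latency.** Section 6.2 says that pembrolizumab events "may occur shortly after the first dose or several months after the last dose of treatment".

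**Start of reporting.** Serious adverse events (SAEs) go to Merck "from the time the consent is signed through 30 days following cessation of treatment" (Section 7.8.4). Sections 7.3.1, 7.7.2 and 7.8.3 start reporting to the Overall PI only after the initial dose.

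**Analysis.** Section 13.5 reports the incidence of each toxicity with 90% exact intervals. It counts from the first treatment with any study agent and names no end of the counting period.

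**The concern.** Confirming the safety of the combination is the first secondary objective, and the protocol itself expects some immune events to begin months after the last dose. It sets a 90-day recording duty for those events but schedules no occasion on which a study clinician asks about them once the end-of-treatment visit is over.

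The patients with no contact at all are those who stop for PD, and this trial expects many of them. The null hypothesis in Section 13.1 is a 3-month progression-free survival rate of 35%. Section 5.9 foresees that some patients will continue treatment elsewhere, but it asks for their records only to date progression or response.

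If late ECIs reach the study only when someone happens to report them, the rates in Section 13.5 mix actively sought events during treatment with passively reported events afterwards. The likely error is a count that is too low.

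**Working it through.** The plan states no figure for late toxicity, so there is none to reproduce. The check compares windows with scheduled contacts and then shows what one missed event does to an estimate.

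**1. Contacts between the end-of-treatment visit and day 90.** Days are counted from the last dose, and I assume the 6-week interval runs from there.

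| Reason for stopping | Planned contact | AE/ECI review listed |
|---|---|---|
| PD | None; survival call at about day 183 (365.25/2) | No |
| Other, without PD | Tumor assessments, about days 42 and 84 | No |
| Toxicity | Follow-up of that event; scans, about days 42 and 84 | Only for the event that led to stopping |

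One caution: the AE row of Table 8 is drawn as a bar, and its right-hand end could not be read in the text available to me. Sections 5.3.3 and 5.9 list no AE review, which is what the table relies on.

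**2. Length of the unreviewed stretch.** Let v be the day of the end-of-treatment visit (at most 30) and t the day new anticancer therapy starts. The ECI window ends at E = min(90, t + 30), and the stretch without a listed review is U = E - v. The values v = 7 and t = 14 are illustrations.

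- No new therapy, v = 30: U = 90 - 30 = 60 days, which is 60/90 or two thirds of the window.
- No new therapy, v = 7: U = 90 - 7 = 83 days.
- New therapy at t = 14, v = 30: E = 44, so U = 44 - 30 = 14 days.
- New therapy at t = 14, v = 7: U = 44 - 7 = 37 days.

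The stretch therefore varies by patient and has no fixed minimum of 60 days.

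**3. An early progressor.** Take doses on days 1 and 22, radiation finished by day 21, and PD at the week-5 scan. General AE collection ends on day 22 + 30 = 52, which is 52 - 21 = 31 days after radiation. The ECI window runs to day 22 + 90 = 112 unless new therapy shortens it. The first survival call falls at about day 22 + 183 = 205.

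**4. What one event does.** These are exact (Clopper-Pearson) 90% intervals, the method in Section 13.5, for a full cohort of 20 and the maximum of 26 (Section 13.2).

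- N = 20: 0/20 gives 0 to 13.9%; 1/20 gives 0.3 to 21.6%.
- N = 26: 0/26 gives 0 to 10.9%; 1/26 gives 0.2 to 17.0%.

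**5. Chance that such an event occurs.** Let q be the risk per patient of a first reportable event in days 31 to 90. The documents give no value, so 2%, 5% and 10% are assumptions. The chance of at least one event is 1 - (1 - q)^N.

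- N = 20: 33%, 64% and 88%, with 0.4, 1.0 and 2.0 events expected.
- N = 26: 41%, 74% and 94%, with 0.5, 1.3 and 2.6 expected.
- N = 13 (0.65 x 20, the share progressed or dead by 3 months under the null): 23%, 49% and 75%.

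These are chances that an event occurs, not that it is missed, because passive reporting will catch some. They also take every patient as at risk for the full 60 days, which new therapy or death would shorten.

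**The case against.** The strongest reply is that the plan is tiered on purpose: all AEs to 30 days, and selected events for longer. That stands. The 30-day and 90-day windows do not contradict each other. A reader might infer that AE collection as a whole stops at 30 days, but the text does not support that. ECIs go on the AE forms to 90 days, ongoing toxicity may be followed, and under Section 7.8.4 an SAE judged related to the Merck product is reportable whenever it comes to the investigator's attention. Section 13.5 sets no 30-day cutoff that would exclude later ECIs.

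A reader might also infer that no patient has any contact in the gap. That is wrong for patients who stop without PD or for toxicity, who are seen about every 6 weeks. The new-therapy rule can shorten the window considerably in the early progressors who matter most here.

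Nor is the size of any undercount shown. The 65% is the null figure and includes deaths; under the target it is 35%. The stated half-life of about 4 weeks says how much drug remains, not how often events occur. For a patient who receives both early doses, the run-in rule looks at events up to cycle 3 day 1, nominally day 43, so days 31 to 90 after the last dose do not affect it.

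On the start of reporting, a reader might infer that an SAE from a baseline biopsy would be lost to the sponsor-investigator. The documents do not go that far. Table 8 marks AE evaluation at screening, and Section 7.8.2 requires AEs to be reported to the Overall PI within 48 hours with no start date. The stated start dates simply differ.

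None of this supplies the missing step. The later routes depend on someone raising the event, and the 6-weekly contacts list tumor assessment only.

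**Conclusion.** The point holds in a limited form. Section 7.8.5 creates a duty to record ECIs to 90 days, or to 30 days after new anticancer therapy if earlier. No AE or ECI review is listed after the end-of-treatment visit, and patients who stop for PD have no planned contact until the survival call at about 6 months. Late ECIs in that group are found passively, so their incidence is likely to be undercounted.

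The direction rests on two assumptions: that some ECIs begin after the last visit, as Section 6.2 says, and that passive reporting misses some of them. The amount cannot be derived. At these sample sizes a single missed event moves the upper 90% limit from 13.9% to 21.6% (N = 20).

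Radiation effects are in a weaker position than immune effects beyond 30 days. Appendix B is a pembrolizumab list, so radiation injury has a 90-day route only if it meets a listed term and grade, such as pneumonitis. The gap is mainly in early progressors, because the 30 days run from the last study intervention and patients who stay on pembrolizumab are observed for longer after radiation.

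The documents do not support extending the window for every AE to 90 days, since Section 7.8.5 covers ECIs only. The primary endpoint is not affected.

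**What to change.** 1. Add to Table 8 and to Sections 5.3.3 and 5.9 a safety contact at day 90 after the last treatment, or at 30 days after new anticancer therapy if earlier. A phone call is enough. It should ask about ECIs and treatment-related events, including radiation-related ones.
2. List AE and ECI review at the existing 6-weekly assessments.
3. State in Section 13.5 that ECI rates are counted over the Section 7.8.5 window.
4. Reconcile the start of SAE reporting to the Overall PI (Sections 7.3.1, 7.7.2 and 7.8.3) with the start of reporting to Merck (Section 7.8.4).

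The general 30-day window for other AEs can stay as it is.

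The cost is one call per patient, a few added AE entries, and reported rates that will probably look slightly less favorable. Clinical management is unchanged.
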